**7.4 Extent of Exposure**

The extent of exposure will be characterized according to the number of subjects exposed, the duration of exposure, and the dose to which they were exposed. Analyses in this section will be performed on the All Treated Subjects.

**7.4.1 Study Therapy**

**Summary:**

Descriptive statistics will be provided by cohort for the following.

- Number of doses, if appropriate
- Duration of therapy (weeks) = (last dose date - first dose date + 7)/7 for Q weekly dosing cohort(s) and (last dose date - first dose date + 21)/7 for Q3 weekly dosing cohort(s)
- Cumulative dose = the sum of all actual doses that a subject received
- Dose intensity = Cumulative dose/Duration of therapy.
- Relative dose intensity (%) = (dose intensity / planned dose intensity)\*100
  - Categories: <50%; 50 - < 70%; 70 - < 90%; 90 - < 110%; ≥ 110%

**Listing:**

- Drug administration of BMS-986148
- Duration of therapy, cumulative dose, dose intensity and relative dose intensity

**7.4.2 Modification of Study Therapy**

**Summary:**

The following will be provided by cohort.

- Number (%) of subjects with dose delay, omission and discontinuation along with the reason
- Number (%) of subjects with dose reduction along with the reason
- Infusion interruptions
  - Number (%) of subjects with at least one infusion interruption along with the reason
  - Number of infusion interruptions per subject
  - Number (%) of subjects with at least one IV infusion rate reduction along with the reason

**Listing:**

- All relevant information on dose modification listed above

**7.4.3 Prior and Concomitant Medications**

Prior and concomitant medications will be coded using the WHO Drug Dictionary. Concomitant medications are defined as medications other than study medications which are taken at any time on-treatment.

**Listing:**

- All prior and concomitant medications

**7.5 Efficacy**

In general, efficacy analyses will be performed for All Treated Subjects unless otherwise specified. Limited efficacy analyses may be performed on the Response-evaluable Subjects (e.g., ORR summary).

Time to event distribution (e.g. progression free survival, overall survival, and duration of response) will be estimated using Kaplan-Meier (K-M) method. When appropriate, the median along with 95% CI will be provided using Brookmeyer and Crowley methodology. Available medians and confidence intervals will also be presented in K-M plots. Rates at fixed time points (e.g. PFSR at 12, 24, 36 weeks) will be derived from the K-M estimates and corresponding confidence intervals will be derived based on Greenwood formula.

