#### **3.1 Study Design and Duration**

This is a Phase 1/2a, open-label study to characterize the safety and tolerability, as well as preliminary efficacy, PK, and PD of BMS-986148 administered alone and in combination with nivolumab in subjects with select advanced solid tumors (pancreatic, ovarian, NSCLC, gastric, or mesothelioma). The study has 3 segments: Part 1 (Phase 1 study - dose escalation), Part 2 (Phase 2a - dose expansion), and Part 3 (BMS-986148 in combination with nivolumab; Part 3A - dose escalation and Part 3B - dose expansion) (see [Figure 3.1-1](#)). All subjects will complete up to 4 study periods: Screening (up to 28 days), Treatment (21 days/cycle Q3W or 28 days/cycle QW), Follow-up (60 or 100 days), and Survival Follow-up (see [Figure 3.1-2](#)). After completing the Follow-up period, subjects will continue to be followed for [REDACTED] up to 2 years from first dose

of study drug for subjects discontinuing study drug prior to 2 years. Subjects receiving study drug for more than 2 years will be followed in the Survival Follow-up period for 6 months from their last treatment date. With Amendment 3, a dose escalation phase will be conducted with BMS-986148 and nivolumab combination therapy (Part 3A). In the BMS-986148 and nivolumab combination therapy dose expansion phase (Part 3B), additional subjects with pancreatic, ovarian, NSCLC, gastric, or mesothelioma will be treated at or below the MTD of the combination dose identified in Part 3A to confirm safety and evaluate anti-tumor activity.

[figure not shown]
The duration of the study is anticipated to be approximately 5 years from the time of the first visit of the first subject to the required Survival Follow-up of the last subject enrolled. The end of the study will occur when the last subject has the last Survival Follow-up visit.

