Concomitant Treatments	X	X	X	X	X	X	X	X	X	X	X f		
Adverse Event Reporting													
Monitor for Non-SAEs	X	X	X	X	X	X	X	X	X	X	X		See note in screening procedures.
Monitor for SAEs	X	X	X	X	X	X	X	X	X	X	X		See note in screening procedures.
PK and Immunogenicity Assessments (See Section 5.5)													
Efficacy Assessments													
Tumor Assessment	At the start of Cycle 3 and then every 2 cycles thereafter (±1 week).									X	X g	X h	See Section 5.4.1.
Tumor Markers (CA125 and CA19-9)	At the start of Cycle 3 and then every 2 cycles thereafter (±1 week).									X	X	X	See note in screening procedures. Baseline sample collection pre-dose on C1D1.
Clinical Drug Supplies													
BMS-986148 Administration	X			X					X				Those supplied by BMS.
Other													
Survival Follow-up												X i	

- a In the event multiple procedures are required at a single time point, the following is a list of procedures from highest priority to low: 1) ECG, 2) PK sampling, and 3) clinical labs.
- b In the Survival Follow-up, subjects discontinuing study drug prior to 2 years will be followed for up to 2 years from first dose of study drug. Subjects treated for > 2 years will be followed for 6 months after EOT.
- c C4D4:  $\pm$  1 day.
- d Ophthalmological examination: 8-point exam (visual acuity, pupils, extraocular motility and alignment, tonometry, visual field, external examination, slit lamp examination and fundoscopy) conducted at baseline and focused exams with visual acuity, slit lamp, and as indicated will be conducted at the end of Cycle 1 (pre-dose Cycle 2), every other cycle, EOT and as clinically indicated during the study.
- e Vital signs will be obtained before the BMS-986148 infusion and then every 30 minutes ( $\pm$  10 minutes) until 30 minutes following completion of the last infusion. If any vital sign is abnormal at the final check, the subject must be observed further for a period of time, as clinically indicated. The start and stop time of the study drug infusion should be documented (start of drug infusion = 0 hour).
- f Only anti-cancer treatments.
- g Only at the 60-day follow-up visit, unless discontinued for disease progression.

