### **5.3 Safety Assessments**

All subjects who receive at least 1 dose of study drug will be evaluated for safety parameters. Additionally, any occurrence of an SAE from the time of consent until 60 days (or 100 days for combination therapy) post discontinuation of study drug dosing will be documented. Any occurrence of nonserious AEs will be collected from first dose of study drug until 60 days (or 100 days for combination therapy) post discontinuation of dosing.

AEs will be coded using the most current version of Medical Dictionary for Regulatory Activities and reviewed for potential significance and importance. Adverse events will be evaluated according to the NCI CTCAE v4.03. Subjects should be followed until all AEs for which no clear alternative cause is identified other than BMS-986148 have recovered to baseline or are deemed irreversible by the investigator. Safety assessments will be based on medical review of AE reports and the results of vital sign measurements, PEs, and clinical laboratory tests. The incidence of AEs will be tabulated and reviewed for potential significance and clinical importance. The schedule of required visits, tests, procedures, and assessments are described in [Table 5.1-2](#) through [Table 5.1-8](#). In limited instances, scheduled events (including events other than safety assessments) can occur outside of the indicated timeframes but the Sponsor should be notified.

Only data for the procedures and assessments specified in this protocol (see [Table 5.1-2](#) through [Table 5.1-8](#)) should be submitted to BMS. Additional procedures and assessments may be performed as part of standard of care; however, data for these assessments should remain in the subject's medical record and should not be provided to BMS unless specifically requested by the Sponsor.

If a subject has a delay in study drug administration for any reason, then assessments and laboratory tests (with the exception of any tests needed to ensure subject safety) should be correspondingly delayed with the exception of tumor assessments (ie, continue scans Q6W for Parts 1A, 2, and 3 and Q8W for Part 1B  $\pm$  1 week regardless of dosing delays).

At baseline, a medical history will be obtained to capture relevant underlying conditions. Baseline signs and symptoms are those that are assessed within 2 weeks prior to subject enrollment. Any new or worsening clinically significant changes must be reported on the appropriate nonserious or serious AE page.

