### 5.4.1 Primary Efficacy Assessment

Tumor measurements with CT and/ or MRI, as appropriate, will be conducted at screening, at the start of Cycle 3, and then every 2 cycles ( $\pm 1$  week) during the treatment phase. Tumor measurements should be conducted earlier, if clinically indicated. Subjects with SD, PR, or CR at the last clinical follow-up visit undergo tumor assessment via CT/MRI scans every 3 to 4 months during the Survival Follow-up ([Sections 8.3.2.2](#) and [8.5](#)) phase until progression or death. Tumor measurements will be collected in all subjects until progression or the subject's

discontinuation from the study as per Table 5.1-2 to Table 5.1-8. Tumor response and progression will be evaluated in this study using RECIST version 1.1 criteria or Modified RECIST for malignant pleural mesothelioma (Appendix 4). Initial response assessment of PR or CR must be confirmed by a consecutive assessment no less than 4 weeks (28 days) later.

At the Sponsor's discretion, de-identified scans and measurements may be collected and reviewed by independent radiologists using RECIST version 1.1 criteria or Modified RECIST for malignant pleural mesothelioma at a later date or at any time during the study.

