### **8.3.2.2 Efficacy**

Efficacy based on RECIST version 1.1 or Modified RECIST for malignant pleural mesothelioma (Appendix 4) will be assessed using the following secondary endpoints:

- Best overall response (BOR): defined as the best response designation over the study as a whole, recorded between the dates of first dose until the last tumor assessment prior to subsequent therapy. CR or PR determinations included in the BOR assessment must be confirmed by a second scan performed no less than 4 weeks after the criteria for response are first met. For those subjects who have surgical resection, only pre-surgical tumor assessments will be considered in the determination of BOR.
- ORR: defined as the total number of subjects whose BOR is either a CR or PR divided by the total number of subjects in the population of interest.
- Duration of response: defined as the time between the date of first response and the subsequent date of objectively documented disease progression or death, whichever occurs first. For those subjects who remain alive and have not progressed or received subsequent therapy, duration of response will be censored on the date of last tumor assessment
- PFS: defined as the time from the first dose of study medication to the date of the first objective documentation of tumor progression or death due to any cause. Subjects who did not progress nor died will be censored on the date of their last tumor assessment. Subjects who did not have any on-study tumor assessments will be censored on the date of the first dose of study medication.
- PFS rate at week 't': defined as the proportion of subjects who remain progression free and surviving at 't' weeks (eg, t=12, 24, and 36 weeks, and following the corresponding planned tumor scan visit). The proportion will be calculated by the product-limit method (Kaplan-Meier estimate) which takes into account censored data.

[figure not shown]

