#### 4.2.2 Efficacy

Efficacy based on RECIST v1.1 or Modified RECIST for malignant pleural mesothelioma will be assessed using the following secondary endpoints:

- **Best overall response (BOR):** defined as the best response designation over the study as a whole, recorded between the dates of first dose until the last tumor assessment prior to subsequent therapy. CR or PR determinations included in the BOR assessment must be confirmed by a second scan performed no less than 4 weeks after the criteria for response are first met. For those subjects who have surgical resection, only pre-surgical tumor assessments will be considered in the determination of BOR.
- **Objective Response Rate (ORR):** defined as the total number of subjects whose best overall response (BOR) is either a CR or PR divided by the total number of subjects in the population of interest.
- **Duration of Response (DOR):** defined as the time between the date of first response and the subsequent date of objectively documented disease progression or death, whichever occurs first. For those subjects who remain alive and have not progressed or received subsequent therapy, duration of response will be censored on the date of last tumor assessment.
- **Progression Free Survival (PFS):** defined as the time from the first dose of study medication to the date of the first objective documentation of tumor progression or death due to any cause. Subjects who did not progress nor died will be censored on the date of their last tumor assessment. Subjects who did not have any on-study tumor assessments will be censored on the date of the first dose of study medication.
- **Progression Free Survival Rate (PFSR) at week ‘t’:** defined as the proportion of subjects who remain progression free and surviving at ‘t’ weeks (t=12, 24, 36, etc). The proportion will be calculated by the product-limit method (Kaplan-Meier estimate) which takes into account censored data.

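### The SAP's 12-, 24- and 36-week PFS rates omit the protocol's after-the-scan qualifier, so a literal reading on Q3W dosing leaves late-window progressions outside the landmark

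*SAP*

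**What the plan says.** SAP 4.2.2 defines the PFS rate at week t as the proportion of subjects "who remain progression free and surviving at" t weeks, with t = 12, 24, 36 and so on, estimated by Kaplan-Meier. SAP 7.5 repeats the landmarks: "Rates at fixed time points (e.g. PFSR at 12, 24, 36 weeks) will be derived from the K-M estimates". Neither section mentions the scan window.

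Protocol 8.3.2.2 defines the same endpoint in nearly the same terms, but its parenthesis reads "eg, t=12, 24, and 36 weeks, and following the corresponding planned tumor scan visit".

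Protocol 5.4.1 schedules on-treatment scans "at the start of Cycle 3, and then every 2 cycles", with a window of one week either side. Protocol 3.1 sets cycles of 21 days for Q3W dosing and 28 days for QW dosing. Protocol 5.3 holds the scan calendar fixed when doses slip: "continue scans Q6W for Parts 1A, 2, and 3 and Q8W for Part 1B".

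Both documents date a PFS event at the first objective documentation of progression, or at death.

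**The concern.** A Kaplan-Meier curve for scan-detected progression falls in steps at the scan dates. If the curve is read on the nominal date of a scan, the answer depends on which side of that date each subject's scan fell. A subject scanned on day 165 whose scan shows progression counts against the 24-week rate. A subject scanned on day 171 with the same finding does not. Early scans keep their progressions inside the landmark and late scans move theirs out, so the net effect is upward.

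The protocol's qualifier guards against this, and the SAP text that programmers will work from lacks it. PFS is a secondary objective in a study without a control arm, so an upward shift in a cohort's rate has nothing within the study to cancel against.

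**Working it through.** **1. Scan calendar.** Scan week = (cycle number − 1) × cycle length, for Cycles 3, 5, 7 and so on.

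- Q3W (21 days): weeks 6, 12, 18, 24, 30, 36. This reproduces the Q6W interval in Protocol 5.3. All three landmarks are nominal scan dates.
- QW (28 days): weeks 8, 16, 24, 32, 40. This reproduces the Q8W interval. Only week 24 is a nominal scan date.

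**2. Inputs not in the documents (assumptions).** Exponential PFS with medians of 2 to 9 months; scan dates uniform over −7 to +7 whole days; no deaths and no censoring in the base case. Neither document gives a PFS median, a distribution or a share of late scans.

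**3. Hand check.** Let S(t) = exp(−ln 2 × t / median). If about half of the week-t scans fall after t, the reading at t is roughly the average of S(t) and S(t − 6). With a 13-week median:

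- Week 12: S(12) = 52.7%, S(6) = 72.6%, average 62.7%, or +10.0 points.
- Week 24: S(24) = 27.8%, S(18) = 38.3%, average 33.1%, or +5.3 points.

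**4. Simulation.** With 400,000 subjects per setting and progression detected at the first scan on or after it occurs, the Q3W week-12 results are:

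| Median PFS (months) | Read at week 12 | True PFS | Difference (points) |
|---|---|---|---|
| 2 | 50.2% | 38.4% | +11.8 |
| 3 | 62.8% | 52.7% | +10.1 |
| 4 | 70.5% | 61.9% | +8.6 |
| 6 | 79.0% | 72.6% | +6.4 |
| 9 | 85.5% | 80.9% | +4.6 |

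Over the same medians the difference is +3.7 to +5.3 points at week 24 and +1.7 to +3.5 at week 36.

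**5. Sensitivity at week 12.**

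- 20% of events are exactly dated deaths: +3.7 to +9.4 points.
- Every scan is 0 to 7 days late: +7.3 to +18.5 points.
- Every scan is on the nominal day and time = event date − first dose date: zero.
- Every scan is on the nominal day but one day is added to that difference: the whole step falls after the landmark. The gap is then S(6) − S(12), or +9.1 to +23.6 points. The SAP does not state the day count for PFS.

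**6. Reading one week later (weeks 13, 25, 37), Q3W.** In the base case the difference falls to between 0.0 and +0.1 points at all three landmarks. With 20% exactly dated deaths it is −0.6 to −0.1. If every scan is late it is −1.8 to −0.2.

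**7. QW.** With 8-weekly scans, weeks 12 and 36 fall between scans and a one-week shift does nothing. At a 3-month median, week 12 reads 65.4% against a true 52.9% whether the curve is read at week 12 or week 13.

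**Scale.** The standard error of a 50% rate with 25 subjects is √(0.5 × 0.5 / 25) = 10 points.

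**The case against.** **The protocol already handles it.** Protocol 8.3.2.2 contains the safeguard, so the shift arises only if the SAP is applied without it. That stands, and it makes this a mismatch between the two documents. But the SAP governs the analysis, and as written it permits a reading at week 12.0.

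**The landmarks are only examples, and windowing rules exist elsewhere.** SAP 7.5 does introduce them as examples, and SAP section 8 invokes the sponsor's EmBARC conventions for windowing in general. Those conventions are not reproduced, and nothing in the documents shows that they move a Kaplan-Meier landmark. The gap is neither proven harmful nor shown to be closed.

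**Documented PFS at week 24.0 is estimated without bias.** For time to documentation as defined, this is correct. The overstatement is relative to the protocol's rate, taken after the planned scan. In the base case of step 6 that rate agrees with true PFS to within 0.1 point, so the differences in step 4 also measure the departure from the protocol.

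**Stronger readings that the documents do not support.** A reader might infer that late-window progressions are lost. They are not: they enter the curve up to a week later, and only the landmark rates shift. A reader might infer that the sponsor deliberately removed the clause. SAP version 1.0 describes two study parts and not three, and its amendment table is empty, so the clause may postdate it. A reader might treat shifts near 20 points as typical. Those need every scan late, or a particular day count, together with short PFS. Finally, landmark rates are not shown to be the main PFS summary, since SAP 7.5 also gives the curves and medians with confidence intervals.

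**Conclusion.** The point holds as a SAP-protocol inconsistency with a predictable direction. On Q3W dosing, a literal reading of SAP 4.2.2 and 7.5 tends to give higher PFS rates than Protocol 8.3.2.2 defines. Under the assumptions in step 2 the size is about +5 to +12 points at week 12, +4 to +5 at week 24 and +2 to +4 at week 36. At week 12 that can match the standard error of a 25-subject cohort; at the later landmarks it is about half of it or less. Actual scan dates, the true PFS distribution and the day count could make it larger or bring it to zero.

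The consequence is limited. There is no formal hypothesis, the Simon futility rules count responders, and no error rate or sample size depends on these rates. The QW part is conditional: SAP 7.2 confines PFS rates to expansion cohorts, and Protocol 3.1.2 makes a QW expansion cohort optional.

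**What to change.** - Carry the qualifier "and following the corresponding planned tumor scan visit" into SAP 4.2.2 and 7.5.
- State that Q3W rates are read once the scan window has closed, for example at 13, 25 and 37 weeks. The protocol does not name these weeks; they are one way to put its clause into practice.
- State the day-count convention for PFS.
- If a QW expansion cohort opens, set its landmarks after its own 8-weekly scans. Week 24 would then be the only one of the three nominal landmarks shared with Q3W.

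This is a wording change that uses the same data. The rates become less favourable. The extra week of exactly dated deaths, or a general tendency to scan late, can pull them slightly low, by under about 2 points in the settings examined.

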**Summary:**

- BOR and ORR outcomes (confidence interval will be calculated by the Clopper-Pearson method) will be tabulated by cohort
- The duration of response (with median [95% CI] and range [min, max]), PFS will be estimated by Kaplan-Meier (K-M) methodology by tumor type for the expansion cohorts only. PFSR (e.g., at 12, 24, 36 weeks) will be similarly estimated based on the Kaplan-Meier methodology

**Figure:**

- Percent change from baseline in target lesions (aka spider plot) by tumor type
- Maximum reduction in baseline target lesions (aka waterfall plot) by tumor type
- Swimmer plot of time to response, duration of response by tumor type

**Listing:**

- Sum of target lesions at each visit, along with corresponding percent change from baseline, percent increase from nadir, and other lesion information will be provided in the order of cohort, subject ID, and assessment study day
- Subject level BOR, duration of response, and PFS will be provided using RECIST v1.1 criteria or Modified RECIST for malignant pleural mesothelioma

**7.6 Safety**

Analysis of safety will be based on All Treated Subjects and presented by dose, dose regimen, and overall (if appropriate).

Adverse events (AEs) will be coded according to the most current version of MedDRA and be graded using the NCI Common Terminology Criteria for Adverse Events (CTCAE) version 4.03. Drug-related AEs are those events with relationship to study drug “Related” as recorded on the CRF. If the relationship to study drug is missing, the AE will be considered as drug-related.

Listing of adverse events will include all enrolled subjects as SAEs and deaths are collected pretreatment. Summaries of adverse events will include (1) events occurring from the first dose date to 60 days (inclusive) after the last dose of BMS-986148 for subjects who are off study treatment and (2) all events occurring from first dose date for subjects who are still on study medication.

When reporting adverse events by CTC grade, summary tables will be provided based on the event with worst CTC grade (independent of relationship to study medication). Subjects will only be counted (1) once at the preferred term (PT) level, (2) once at the system organ class (SOC) level, and (3) once in the ‘Total subject’ row at their worst CTC grade, regardless of SOC or PT.

The analysis of laboratory results will be based on All Treated Subjects. Laboratory results will be categorized according to NCI CTCAE (version 4.03) grade. Baseline is defined as the last non-missing measurement prior to the first dosing date and time. Summaries of laboratory results include baseline and (1) post-baseline results up to 60 days (inclusive) after the last dose of BMS-986148 for subjects who are off study treatment and (2) all available post-baseline results for subjects who are still on study medication.

